3. PRIMARY OBJECTIVE

To study the use of ibrutinib starting between day 60 and day 90 after allogeneic HCT until 12 months post HCT to improve the PFS at 12 months post HCT by 25% compared to historical controls. The sample size is designed to address this primary endpoint.

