 - Peripheral blood samples on all patients should be sent for Immunoseq for T-cell receptor and immunoseqMRD analysis. See the Laboratory Manual for sample acquisition, processing and shipping logistics.
 - Research: A peripheral blood sample will be collected for CyTOF analyses. See the Laboratory Manual for detailed instruction on collection, processing and shipping.

- Research: Toxicity assessment for ibrutinib
 - Research: Toxicity assessment will be done. In addition, toxicity assessment will be done 30 days after cessation of ibrutinib.
 - Concomitant medication use will be recorded

HCT outcome (from 1 yr. post HCT until 2 yr. post HCT)

- Chronic GVHD assessment:
 - Standard of care: assessment per institutional standard.
 - If new diagnosis of chronic GVHD or new organ involvement, coordinating center needs to be informed within 1 month of occurrence. NIH 2014 diagnosis and scoring forms will be used. See the Clinical Assessment Manual for details.
- Disease reassessment:
 - Standard of care: assessment per institutional standard
 - If evidence of progression or relapse, coordinating center needs to be informed within 1 month of occurrence
 - Suspected relapse
 - Research: Although not required by protocol, BM aspirate in patients with active marrow disease will be sent to the coordinating center. See the Laboratory Manual for detailed instruction on collection, processing and shipping.
 - Research: Although not required by protocol, tumor biopsy performed for suspected relapse should be collected and sent to coordinating center. See the Laboratory Manual for detailed instruction on collection, processing and shipping.
- Survival
 - Standard of care: At months 18 and 24 post HCT, coordinating center will be informed of survival status: alive without disease, alive with disease (if new relapse/progression, date of event). If patient died between month 12 and 24, coordinating center will be notified within 2 weeks of event, with date and cause of death (disease or non-relapse)

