24. STATISTICAL ANALYSES PLAN

24.1 Analysis Plan

The statistical analysis plan will address the primary aim: To study the use of ibrutinib starting between day 60 and day 90 after allogeneic HCT until 12 months post HCT to improve the PFS at 12 months post HCT by 25% compared to historical controls. This will be restricted to cohort A which includes the diagnoses of CLL and MCL, only.

- PFS is defined as time to progression, or relapse of the underlying disease for which transplant was undertaken, or death from any non-relapse causes, starting from the date of stem cell transplant (SCT).
- We will estimate the 12-month PFS rate with a 95% confidence interval using the method of Kaplan-Meier and using the Greenwood variance estimator, and we will compare this estimate with the rate in the historical controls.
- Historical data
 - In a study by Sobecks et al⁵³, the outcomes of patients with CLL after ablative (n=163) and reduced intensity conditioning (RIC) 134 were reported. Outcomes were stratified based on when the HCT occurred (< 2000, or ≥ 2000). We expect the majority of patients with CLL on the proposed study to be undergoing RIC allo HCT, thus relevant data (≥ 2000 and RIC allo HCT) are taken into account for sample size analyses. One year PFS was 62% (95% CI 51-72).
 - In a study by Urbano-Ispizua et al⁵⁴, the outcomes of patients with MCL undergoing ablative (n=149) and RIC (n=351) allo-HCT was reported. The 1y PFS for patients with MCL (personal communication, CIBMTR) was 52% (95% CI 47-56)
- The proportion of patients with CLL and MCL enrolling in this study will not be known at the start of the study or be controlled for during the accrual period. Thus, we studied the impact on power of varying proportions of these two diagnoses on outcome for a given effect size.
- We will compare our overall PFS rate with the weighted average of the historical rates in CLL and MCL, using the proportion of our sample with each of these two diagnoses as the weights.

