24.2 Sample Size

The following table reflects the power and effect size, if we enroll 65 patients with varying proportion of the diagnoses. **These calculations are based on the maximum likelihood estimator (MLE) for the mean survival time assuming exponentially-distributed PFS⁵³ using the cube-root transformation of the MLE as suggested by Spratt⁵⁴. The one-year survival probability can be calculated once the distribution is specified.** The following test statistic has a standard normal distribution:

$$\frac{\hat{\phi} - \phi}{(\hat{\phi}^2/9\hat{Q})^{1/3}} \sim N(0,1),$$

where $\hat{\phi} = \hat{\theta}^{-1/3}$, $\hat{\theta}$ is the MLE for the PFS mean, and $\hat{Q} = \sum(1 - e^{-L_i/\hat{\theta}})$.

This is a single arm phase two study. Patients will be accrued uniformly over two years, and then followed for two years. The power calculations are based on derivations from Lawless⁵³ with a cube-root transformation of the maximum likelihood estimate (MLE), as suggested by Spratt⁵⁴. This is implemented in the online calculator (tool of One Arm Survival) found at <https://stattools.crab.org> which is provided by the SWOG Statistical Center. Thus, 65 patients will give us at least 84% power to detect an effect size of 25% improvement in progression-free survival at 1 year compared to the estimated historical control rate, for varying proportions of patients with CLL and MCL. The following table reflects the power and effect size, if we enroll 65 patients with varying proportion of the diagnoses.

Table: Power achieved for a sample of 65 patients for different effect sizes using a 2-sided parametric test with level 0.05, assuming on 2 years of uniform accrual and 2 years of follow-up time.

	%CLL	%MCL	1 year PFS Historical Control	1 year PFS Treated	Power
20%	30	70	0.55	0.660	74
	40	60	0.56	0.672	76
	50	50	0.57	0.684	78
	60	40	0.58	0.696	80
	70	30	0.59	0.708	83
25%	30	70	0.55	0.688	91
	40	60	0.56	0.700	92
	50	50	0.57	0.713	93
	60	40	0.58	0.725	95
	70	30	0.59	0.738	96
30%	30	70	0.55	0.715	98
	40	60	0.56	0.728	98
	50	50	0.57	0.741	99
	60	40	0.58	0.754	99
	70	30	0.59	0.767	99

In addition, cohort B will include 10 patients (FL and HD). There is no formal sample calculation for cohort B.

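### The power in 24.2 belongs to an exponential test with 2–4 years of follow-up per patient, while 24.1 plans a 12-month Kaplan-Meier comparison without naming a test, interval scale or success rule

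*Combined protocol and SAP*

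**What the plan says.** Section 3 sets 12-month PFS as the primary endpoint and adds: "The sample size is designed to address this primary endpoint".

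Section 24.1 describes the analysis: "We will estimate the 12-month PFS rate with a 95% confidence interval using the method of Kaplan-Meier and using the Greenwood variance estimator". The comparison follows: "We will compare our overall PFS rate with the weighted average of the historical rates in CLL and MCL". The weights are the observed diagnosis proportions. The section gives no test, no scale for the interval (plain, log or log-log) and no criterion for success.

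Section 24.2 describes another procedure, based on the maximum likelihood estimate of an exponential mean with a cube-root transformation. It links this to the endpoint in one sentence: "The one-year survival probability can be calculated once the distribution is specified". The follow-up is stated as "Patients will be accrued uniformly over two years, and then followed for two years", and the table title says "using a 2-sided parametric test with level 0.05, assuming on 2 years of uniform accrual and 2 years of follow-up time". For the 25% effect the table prints 91, 92, 93, 95 and 96% across 30–70% CLL. The text says "65 patients will give us at least 84% power to detect an effect size of 25% improvement in progression-free survival at 1 year".

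The last follow-up block in Section 20 is headed "HCT outcome (from 1 yr. post HCT until 2 yr. post HCT", and Section 21.1 also ends follow-up for progression and survival at 2 years after transplant.

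**The concern.** A power figure is informative only for the test that will be run. An exponential test uses every event over the whole follow-up, whereas a 12-month Kaplan-Meier estimate uses only what happens up to month 12. If the second is the primary analysis, the table overstates what 65 patients can show.

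For the 25% effect, the chance of missing a real improvement reads as 4–9% in the table and at most 16% in the text. Under the 24.1 comparison it would be about 22–47%. Under the exponential test with 2 years per patient it would be about 9–16%. Because no primary test is named, two analyses with different power remain open after the data are seen.

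**Working it through.** **Inputs.** n = 65; two-sided level 0.05; accrual and follow-up as in 24.2. The 24.1 rates are 62% for CLL and 52% for MCL, so the historical rate is 0.62w + 0.52(1 − w), or 0.55 to 0.59 for w = 30% to 70% CLL. The target rate is 1.25 times that.

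**Step 1: reproduce the table.** Put λ = −ln(1-year PFS), φ = λ^(1/3), Q = 65 × (1 − E[exp(−λL)]) and SE = φ₁/(3√Q), where subscript 1 is the target. Power = Φ((φ₀ − φ₁)/SE − 1.96). Two years of uniform accrual plus two more years give L uniform on 2–4 years.

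At 50% CLL (0.57 against 0.7125):
- λ₀ = 0.5621 and λ₁ = 0.3390, so φ₀ = 0.8253 and φ₁ = 0.6973.
- E[exp(−λ₁L)] = 0.3687, so Q = 41.04 and SE = 0.0363.
- (φ₀ − φ₁)/SE = 3.53, so power is 94.2% (table: 93%).

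All 15 rows agree within 2 points by formula. Simulation of the same test (40,000 runs) agrees within 0.7 points. The table is therefore identified as this test with 2–4 years per patient.

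The denominator as printed has exponent 1/3. A standard error needs 1/2, which is what is used here. Taken literally, the printed form gives about 0.5–1.4% power.

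**Step 2: same test, 2 years per patient.** At 50% CLL, Q = 32.00, SE = 0.0411 and the ratio is 3.12, giving 87.6%. Over the five mixes, power is 84.1–90.7% (25% effect), 64.9–73.7% (20%) and 94.9–97.9% (30%).

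**Step 3: 12-month Kaplan-Meier comparison.** With no loss before month 12, the estimate is p = x/65 and the Greenwood SE is s = √(p(1 − p)/65). 24.1 gives no rule, so success is assumed to mean a lower 95% limit above the historical rate. The lower limits are:
- plain: p − 1.96s
- log: p·exp(−1.96s/p)
- log-log: p raised to the power exp(1.96s/(p·|ln p|))

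Find the smallest x that succeeds, then take exact binomial tails for power and one-sided error. At 50% CLL:
- plain needs 45 (limit 0.580; 44 gives 0.563)
- log needs 44 (0.572; 43 gives 0.556)
- log-log needs 46 (0.581; 45 gives 0.565)

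**Results, 25% effect.** Power in %; brackets give the smallest successful count and the one-sided error in %.

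| CLL % | Historical | Table | Exp. 2–4 y | Exp. 2 y | Plain | Log | Log-log |
|---|---|---|---|---|---|---|---|
| 30 | 0.55 | 91 | 91.5 | 84.1 | 63.0 (44; 2.6) | 72.4 (43; 4.5) | 52.7 (45; 1.4) |
| 40 | 0.56 | 92 | 92.9 | 85.9 | 71.0 (44; 3.7) | 71.0 (44; 3.7) | 61.3 (45; 2.0) |
| 50 | 0.57 | 93 | 94.2 | 87.6 | 69.5 (45; 3.0) | 78.2 (44; 5.2) | 59.5 (46; 1.6) |
| 60 | 0.58 | 95 | 95.3 | 89.2 | 77.0 (45; 4.2) | 77.0 (45; 4.2) | 68.0 (46; 2.3) |
| 70 | 0.59 | 96 | 96.3 | 90.7 | 75.8 (46; 3.4) | 75.8 (46; 3.4) | 66.4 (47; 1.8) |

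The Kaplan-Meier columns lie 15–38 points below the table, row by row. They are not monotone because the counts are discrete. The log-log counts equal those of an exact one-sided 2.5% binomial test.

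For the other effects, log-log gives 34–48% (20%) and 71–84% (30%), against 74–83% and 98–99% in the table.

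**Step 4: source of the gap.** The exponential test cut at month 12 has 62.5–70.3% power for the 25% effect. Most of the difference therefore comes from counting events after month 12.

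**Step 5: early loss.** With 5–10% random loss in year 1 (assumed; 20,000 simulated runs), the three intervals stay between 54% and 78%.

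**The case against.** The strongest reply is that the exponential test is the primary test. Section 24.2 is the only place that gives a statistic, a level and sidedness, and it ties the model to one-year survival. Section 24.1 can then be read as estimation with a descriptive comparison, and sizing a single-arm phase 2 trial under an exponential model is a familiar simplification. This reading is open, so the documents do not support a reader's inference that the table is simply false or that the trial has 53–78% power as a matter of fact. What remains is that 24.1 never mentions the test, the constant-hazard assumption is not carried into the analysis, and the table needs longer follow-up than Sections 20 and 21.1 provide.

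The follow-up sentence in 24.2 might itself mean two years per patient. That would remove the conflict with Sections 20 and 21.1, but the table would then not match its own assumption.

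Three other stronger readings also fail:
- The 84% in the text does not contradict the table, because it is a floor.
- The 53–78% range is not due to the interval alone. Its low end is log-log at 30% CLL and its high end is log at 50% CLL. At a 50/50 mix the intervals span 60–78%.
- The exponent 1/3 does not show that the computation was wrong. The table reproduces with 1/2, so a misprint or a PDF-reading error is likely.

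It is also fair to say that the upper Kaplan-Meier figures are not like for like: the log interval's 78% carries a 5.2% one-sided error.

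**Conclusion.** The concern holds as an unnamed primary test with power shown for only one candidate. Under either reading a printed figure needs correction, unless follow-up is really 2–4 years per patient and the exponential test is primary.

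- **Kaplan-Meier comparison primary:** power for the 25% effect is 53–68% (log-log), 63–77% (plain) or 71–78% (log), all below the table and below 84%. Of the three, only log-log keeps one-sided error within 2.5% at every mix.
- **Exponential test primary, 2 years per patient:** 84–91% for the 25% effect. The text stands, and the 25% rows are about 5–7 points too high (91 − 84.1 = 6.9; 96 − 90.7 = 5.3).

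The Kaplan-Meier figures rest on the assumed success rule, a historical rate treated as fixed, and no loss before month 12. The exponential figures also treat the historical rate as fixed and need a constant hazard.

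**What to change.** Name one primary test, interval scale and success rule in 24.1, and print only that test's power in 24.2.

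- **If the 12-month Kaplan-Meier comparison is primary:** use the log-log interval (or an exact binomial test if there is no early censoring). Restate power as 53–68% (25% effect), 34–48% (20%) and 71–84% (30%), with the fixed-historical-rate and no-early-loss assumptions written down. This tests the stated endpoint without assuming a distribution.
- **If the exponential test is kept:** say so in 24.1 and reconcile the follow-up in 24.2 with Sections 20 and 21.1. If it is 2 years per patient, restate power as 84–91% (25%), 65–74% (20%) and 95–98% (30%). If 2–4 years is meant, the table can stand, but Sections 20 and 21.1 must provide that follow-up. Declare the constant-hazard assumption, keep the Kaplan-Meier estimate as a sensitivity analysis, and check the exponent in the printed denominator.

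The change is to wording and stated figures, with no change in enrolment. The cost is a less favourable stated power.

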21. SUBJECT WITHDRAWAL

21.1 Withdrawal from Study Treatment

Study treatment will be withdrawn if:

- Patient experiences relapse or progression of underlying disease while on ibrutinib, and further continuation is not felt to be beneficial.
- Unacceptable toxicity: an intercurrent illness or adverse event that prevents further ibrutinib administration for more than 28 continuous days
- Non-compliance with taking ibrutinib or with following protocol
- Investigator decision
- Withdrawal of consent for treatment by subject
- Subject becomes pregnant
- Study termination by sponsor-investigator

All subjects, regardless of discontinuation of study treatment will undergo end of study visit and be followed for progression and survival until 2 y post HCT by imaging (CT scan and/or PET scan or other imaging) or other modalities per the discretion of the treating physician.

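### The power table assumes 2 to 4 years of follow-up per patient, but the protocol stops at 24 months post HCT; for the 25% effect the printed 91–96% becomes 84–91%, even for the plan's own exponential test

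*Combined protocol and SAP*

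**What the plan says.** Section 24.2 sizes cohort A at 65 using the "maximum likelihood estimator (MLE) for the mean survival time assuming exponentially-distributed PFS", with a cube-root transformation. On timing it states: "Patients will be accrued uniformly over two years, and then followed for two years". The table caption repeats that timing, "assuming on 2 years of uniform accrual and 2 years of follow-up time", and names the test as parametric, two-sided, at the 5% level. For the 25% effect it prints 91, 92, 93, 95 and 96% as the CLL share rises from 30% to 70%. The sentence introducing it gives a different floor: "Thus, 65 patients will give us at least 84% power to detect an effect size of 25% improvement".

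The conduct sections limit follow-up. Section 21.1 says all subjects will "be followed for progression and survival until 2 y post HCT". The last follow-up period in Section 20 is "HCT outcome (from 1 yr. post HCT until 2 yr. post HCT", with survival status reported at months 18 and 24. Both study tables in Section 22 end at month 24. Section 24.1 counts PFS from the date of transplant, so 24 months post HCT is also the latest PFS censoring time.

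**The concern.** In a one-arm exponential test, power depends on the expected number of events, and so on how long each patient is watched. Two years of accrual followed by two years of follow-up, entered into a standard calculator, means the first patient is followed for 4 years, the last for 2, and the average is 3. If the protocol stops each patient at 24 months, the extra person-time and events are never collected and the table overstates power.

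The two power figures for one effect, 84% in the text and 91% as the table's minimum, point the same way: they do not come from the same follow-up assumption. Section 3 says the sample size is designed for the primary endpoint, so its justification should rest on data the trial will have.

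**Working it through.** **Inputs.** From 24.2: n = 65, two-sided 0.05, exponential PFS, and the table's historical and treated 1-year PFS values. The historical values are weighted averages of 62% (CLL) and 52% (MCL) from 24.1; for example 0.30 × 62 + 0.70 × 52 = 55.0%. Follow-up is either the table's (2 + 2 years) or the protocol's (24 months).

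**Formulas.** λ = −ln(1-year PFS); φ = λ^(1/3); SE = φ₁ / (3√Q), with Q the expected number of events under the treated rate; power = Φ[(φ₀ − φ₁)/SE − 1.96].

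- Follow-up uniform on 2 to 4 years: Q = 65 × [1 − (e^(−2λ) − e^(−4λ))/(2λ)]
- Every patient censored at 2 years: Q = 65 × (1 − e^(−2λ))

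The statistic as printed carries the exponent 1/3 on the variance term. I used the square root, which is what reproduces the table. No dropout is allowed for; the plan states none.

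**One row in full: 25% effect, 30% CLL, 0.55 against 0.688.** λ₀ = 0.5978, λ₁ = 0.3740, φ₀ = 0.8424, φ₁ = 0.7205. Results carry full precision.

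- 2 to 4 years: Q = 43.3, SE = 0.0365, ratio 3.343, power Φ(1.383) = 91.7%. The table prints 91.
- 24 months: Q = 34.2, SE = 0.0410, ratio 2.971, power Φ(1.011) = 84.4%.

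**All rows**, CLL share 30/40/50/60/70%:

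| Effect | Printed | 2 to 4 years per patient | Censored at 24 months |
|---|---|---|---|
| 20% | 74/76/78/80/83 | 74.4/76.8/79.1/81.3/83.5 | 64.9/67.1/69.3/71.5/73.7 |
| 25% | 91/92/93/95/96 | 91.7/92.9/94.3/95.3/96.4 | 84.4/85.9/87.9/89.2/90.9 |
| 30% | 98/98/99/99/99 | 98.3/98.7/99.1/99.4/99.6 | 94.9/95.8/96.6/97.3/97.9 |

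With 2 to 4 years of follow-up, all 15 rows match the printed values to within 1.4 points. With 24 months, the 25% rows miss by about 5 to 7 points. The table therefore rests on 2 to 4 years per patient.

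Expected events under the 25% effect fall from 43.3 to 34.2 in the lowest-power row and from 38.5 to 29.6 in the highest.

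**Robustness.** Using the null variance for the critical value and the alternative variance for power, the 24-month figures for the 25% rows are 83.6, 85.3, 87.4, 89.0 and 90.8%. Simulation with 100,000 trials per scenario gives 84.0–84.4, 85.8, 87.6, 89.3 and 90.9%. Unrounded treated rates (0.6875 in place of 0.688, and so on) give 84.1–90.7%.

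**The case against.** **The design conclusion does not change.** The sentence that justifies 65 patients claims a floor of 84% for the 25% effect. That remains true under 24-month follow-up, and power for the target stays above 80% at every mix. The 20% rows are sensitivity rows. All of this stands: the exponential test is not underpowered for the target and the sample size need not move. It does not rescue the table. In the 25% rows the printed type II error is 9% against about 16% at one end and 4% against about 9% at the other.

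**Two years of follow-up may mean two years for each patient.** The sentence in 24.2 can be read that way, and would then agree with Sections 20 to 22. The printed numbers would still be wrong, because that reading gives 84.4% where the table says 91%.

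**The match between 84% and the 24-month limit may be chance.** Two years of accrual plus one further year gives 83.6% in the lowest row, which is nearly as close. The origin of the 84% cannot be settled from the documents. The disagreement between text and table does not depend on it.

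**The planned analysis is not this test.** Section 24.1 plans a Kaplan-Meier estimate at 12 months with Greenwood variance, to which follow-up after month 12 adds nothing. With no censoring before month 12 and a fixed historical rate, a Wald comparison on the plain scale has power of about 67–77% for the 25% rows. This is a real and separate problem. Correcting the follow-up alone leaves a table that describes the parametric test only. The caption does say the test is parametric, and the table is wrong for that test.

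**Conclusion.** The point holds. The power table in 24.2 relies on follow-up that the protocol does not plan. For the exponential test it describes, power for the 25% effect is 84–91%, where 91–96% is printed; for the 20% effect 65–74%, where 74–83% is printed; and for the 30% effect 95–98%, where 98–99% is printed. Two of the 20% rows are printed at 80% or more, and none exceeds 74% under the protocol's follow-up. Section 24.2 also gives two minimum powers for the same effect.

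These figures assume exponential PFS, 65 evaluable patients, full follow-up to 24 months and a fixed historical rate. Any earlier loss to follow-up would lower them. The error lies in the stated power and in the agreement between sections; it does not by itself call for more patients.

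**What to change.** Recompute the table with every patient administratively censored at 24 months post HCT:

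- 20% effect: 65, 67, 69, 72, 74
- 25% effect: 84, 86, 88, 89, 91
- 30% effect: 95, 96, 97, 97, 98

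State in the caption, and in the accrual sentence above the table, that each patient is followed to 24 months post HCT. Make text and table quote the same minimum for the 25% effect, 84%. Keep the label saying that these are powers for the parametric test, so they are not read as powers for the 12-month Kaplan-Meier comparison.

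The cost is one table, its caption and a sentence. The stated power becomes less favourable; no patients, visits or procedures are added.
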